# 12.3. Statistical Analyses

Unless otherwise indicated, all testing of statistical significance will be 2-sided, and a difference resulting in a P value of less than or equal to 0.05 will be considered statistically significant.

Version: 2.0, 17NOV2015 Page 70 of 99

Furthermore, the baseline will be the last assessment before the first dosing of the study medication.

Summary statistics will be provided for the variables described in the following sections. For continuous variables, these statistics will typically include the number of subjects, mean, standard deviation (SD), median, minimum, and maximum. For categorical variables, these statistics will typically include the number and percentage of subjects in each category.

#### 12.3.1. Study Subjects and Demographics

#### 12.3.1.1. Subject Disposition and Discontinuations

The numbers of subjects randomized, completing, and discontinuing, along with reasons for discontinuation, will be tabulated overall and by CAM2038 treatment group (24 mg and 32 mg groups) and sequence. The number of subjects in each analysis population will be reported.

#### 12.3.1.2. Protocol Deviations

Major protocol deviations will be classified and documented before database lock and will be discussed in the CSR. All protocol deviations, both minor and major, will be presented in a data listing.

## 12.3.1.3. Demographics and Other Baseline Characteristics

Demographic and baseline characteristics (including age, sex, race, weight, and height) will be summarized for each treatment group, sequence, and for the overall population by descriptive statistics. Medical history and clinical laboratory tests will be listed.

Prior and concomitant medications will be summarized by treatment group and sequence by the number and percentage of subjects taking each medication, classified using World Health Organization Drug Dictionary Anatomical Therapeutic Chemical classes and preferred terms.

#### **12.3.2. Exposure**

Study drug administration will be summarized in terms of exposure in day (last dose date – first dose date +1). Descriptive statistics for these quantities, including the mean, SD, minimum, and maximum, will be provided by treatment group.

#### 12.3.3. Efficacy Analyses

Efficacy variables will be summarized and analyzed using both Completer and ITT Populations unless otherwise specified. The primary analyses will be based on the Completer Population.

#### 12.3.3.1. Primary Efficacy Analyses

The primary efficacy variable will be  $E_{max}$  of Drug Liking VAS. This variable will be analyzed via a mixed model including subject, challenge dosing (A=0 mg, B=6 mg, or C=18 mg), Period (1, 2, or 3 to indicate first, second, or third day of each challenge session), challenge session (1, 2, 3, or 4), where subject will be treated as random effects and the remaining parameters fixed effects. The estimated treatment effects, differences in treatment effects (test dose – the reference

Version: 2.0, 17NOV2015 Page 71 of 99

dose of 0 mg), 95% confidence intervals of the differences will be presented. Blockade effects will be claimed if upper bound of the treatment difference is  $\leq 11$ .

#### 12.3.3.2. Secondary Efficacy Analyses

The secondary endpoints will include:

- Emax of High VAS
- Emax of Good Effects VAS
- Emax of Bad Effects VAS
- Emax of Sedated VAS
- Emax of Any Effects VAS
- Emax of Desire to use VAS

These variables will be analyzed using the similar methods discuss for the primary efficacy variable analyses.

COWS and OOWS scores will be summarized.

#### 12.3.4. Safety and Tolerability Analyses

Safety analyses will be conducted using data from the Safety Population (as defined in Section 12.2).

Safety and tolerability will be assessed through TEAEs; hematologic and laboratory parameters; and vital signs measurements.

No formal statistical comparisons will be performed for safety endpoints.

#### 12.3.4.1. Adverse Events

Adverse events will be coded by system organ class (SOC) and preferred term using the Medical Dictionary for Regulatory Activities (MedDRA) reporting system. Treatment-emergent AEs are defined as any of the following:

- Non-serious AEs with onset on the date of first dose of treatment with the study drug through discharge or Early Termination, whichever occurs first;
- Serious AEs with onset on the date of first dose of treatment with the study drug through 30 days after discharge or Early Termination, whichever occurs first;
- AEs that start before the start of treatment but increase in severity or relationship at the time of or following the start of treatment through discharge or Early Termination, whichever occurs first.

The number and percentage of subjects with TEAEs will be displayed for each treatment group. During the Qualification Phase subjects TEAEs will be displayed by IR morphine 30 mg

Version: 2.0, 17NOV2015 Page 72 of 99

treatment or by hydromorphone treatment groups i.e., 0 mg 6 mg or 18 mg - on the days of hydromorphone challenges. During the Treatment Phase, TEAEs will be displayed by CAM2038 q1w relevant dose and hydromorphone relevant dose i.e., 0 mg 6 mg or 18 mg - on the days of hydromorphone challenges. TEAEs will be displayed by SOC and preferred term. Additionally, TEAEs will be tabulated for each treatment group by severity and by relationship to the study drug. A listing of SAEs will be provided if applicable.

If an AE is considered to be caused by a drug, the Investigator will note which drug caused the AE.

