### 7. INVESTIGATIONAL PLAN

# 7.1. Overall Study Design and Plan

This is a multi-site, randomized, double-blind, repeat-dose Phase 2 study to evaluate the degree and duration of action of multiple doses of CAM2038 q1w in blocking the effects of a mu opioid agonist (hydromorphone) in patients with moderate or severe opioid use disorder. The study will involve 4 phases: Screening, Qualification, Treatment, and Follow-up.

Within 4 weeks of initiating screening, subjects will be admitted to a clinical research unit (CRU) for the Qualification Phase. Following check in to the CRU, subjects will be transitioned to a short-acting oral opioid, IR morphine 30 mg, (administered 4 times daily [QID]), for a minimum of 3 days and a maximum of 7 days (Qualification Phase described in detail in Section 7.1.2). One additional dose of IR morphine 30 mg may be administered for the first 3 days of stabilization, as needed, at the investigator's discretion. After stabilization on IR morphine 30 mg, all subjects will complete a 3-day Qualification/Baseline Hydromorphone Challenge Session which will involve IM administration of 3 doses of hydromorphone (Treatment A: 0 mg [placebo], Treatment B: 6 mg and Treatment C: 18 mg) administered once daily (Day -3, Day -2, and Day -1) in a randomized, double blind, crossover manner, with each hydromorphone administration separated by approximately 24 hours (described in detail in Section 7.1.4).

Following the Qualification/Baseline Hydromorphone Challenge Session, eligible subjects will receive CAM2038 q1w at doses of 24 mg or 32 mg (randomized in a 1:1 ratio to 1 of 2 groups). Subjects will receive once weekly SC injections of CAM2038 q1w for 2 weeks (injections on Day 0 and Day 7) and will remain inpatient in the CRU for up to 25 days (including Qualification Phase), during which time 4 Hydromorphone Challenge Sessions (3 consecutive days each) will be conducted on Days 1 to 3, Days 4 to 6, Days 8 to 10, and Days 11 to 13, respectively. Safety and pharmacodynamic assessments will be performed on each day of the Hydromorphone Challenge Sessions at multiple timepoints beginning at pre-dose until approximately 5 hours post-dose. Plasma samples to quantify BPN and norbuprenorphine levels will also be obtained approximately 60 minutes prior to hydromorphone dosing on each day of the Hydromorphone Challenge Sessions.

Subjects will be discharged on Day 14 and a follow-up phone interview will be conducted on approximately Day 21.

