### 7.1.5. Follow-up Phase

Following the last day of the Treatment Phase (i.e., Day 14), plasma BPN levels are expected to be approximately 1.4 to 1.8 ng/mL and to gradually taper off; therefore, subjects are not expected to experience immediate withdrawal effects at the time of discharge. A follow-up telephone interview will be conducted approximately 7 days after discharge from the CRU to obtain information on any safety issues including withdrawal effects.

Subjects will participate in the study for approximately 7 weeks, from Screening to Follow-up.

An overview of the study design is provided in Figure 2.

Study assessments and procedures will be performed at the visits and time points outlined in the Schedule of Assessments.

Section 10 provides additional information on the baseline, safety, and pharmacodynamic procedures and assessments included in the study. Pharmacodynamic endpoints are described in Section 10.7. Statistical analysis is described in Section 12.

Version: 2.0, 17NOV2015 Page 35 of 99

Figure 2 Overview of Study Design

Screening	Qualif	ication		Treat	ment		Follow-up
	Inpatient Start	Qualification/ Baseline Challenge	q1w Dose 1	Week 1: Q1w Challenge	q1w Dose 2	Week 2: Q1w Challenge	
			CAN	Challenge 1: Days 1 to 3 Challenge 2: Days 4 to 6 2038 q1w 32mg		Challenge 3: Days 8 to 10 Challenge 4: Days 11 to 13 Discharge: Day 14	
	MS-IR (QID)	morning of the Qual	CAN	12038 q1w 24 mg			
		Challenge					
2 weeks	Day -10, Day -9, Day -8, Day -7, or Day -6 to Day -4	Days - 3 to -1	Day 0	Days 1 to 6	Day 7	Days 8 to 14	Day 21

IR = immediate-release; MS = morphine sulfate; q1w = once weekly dosing; R = randomization

**Table 4** Schedule of Assessments

Screening		Inpatient Qualification Phase				Follow-up Phone Call				
Visit:	1 2									
Day:	-39 to -11	-10, -9, -8, -7, OR -6	-9, -8, -7, -6, OR -5 to -4	-3 to -1	0	1 to 3 & 4 to 6	7	8 to 10 & 11 to 13	14/ ET	21
Assessment										
Informed Consenta	X									
Eligibility Criteria Review b	X	X								
Medical and Medication History	X	Xc								
DSM-V	X									
Physical Examination (including BMI)	X d	Xe							Xe	
Serology panel (optional)	X									
Concomitant Meds/Procedures	X	X	X	X	X	X	X	X	X	X
ECG	X	X			Xf		Xf		X	
Urine Drug Screen g	X	X								
Breath Alcohol Test	X	X								

<sup>a Subjects must voluntarily provide written informed consent prior to any study-related procedures being performed.

Version: 2.0, 17NOV2015 Page 37 of 99

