## 10.4.1.1. Adverse Event Reporting

All AEs (except for withdrawal symptoms, see below) must be entered on the AE CRF, regardless of causality or severity. AEs include new AEs, worsening baseline conditions, clinically significant laboratory findings, disease-related signs and symptoms that were not present at baseline, and any events or findings that the Investigator feels are clinically significant. Withdrawal symptoms will be captured via specified assessments and should not be recorded as AEs.

Disease-related signs and symptoms that are present at baseline should not be recorded as AEs unless they worsen in severity or increase in frequency, but rather should be considered and recorded as pre-existing conditions.

Information collected concerning AEs will include the following:

- Name of the event
- Onset date
- Resolution date
- Severity (i.e., mild, moderate, or severe)
- Relationship to study drug
- Action and outcome
- Seriousness of event

All AEs will be documented and followed from the time the subject has signed the ICF until 14 days after the Follow-up Visit (or 30 days after Early Termination). Serious AEs and AEs that have been designated as possibly related to study drug will be followed until resolution or stabilization. At least 3 attempts will be made to contact the subject and after 3 unsuccessful attempts, a certified letter will be sent to the subject address that was provided to the site.

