11.2 ADVERSE EVENTS

Each AE and SAE term recorded on the case report forms (CRFs) by primary system organ class (SOC) and will be mapped to a preferred term using the MedDRA dictionary. The investigator will assess AE severity and relationship to the study treatment.

A treatment emergent adverse event (TEAE) is defined as any AE with an onset date on or after date of randomization, or any ongoing event on the date of first dose that worsens in severity after date of randomization. Only TEAEs with an onset date prior to date of last dose + 30 days will be tabulated in summary tables. For the purpose calculating treatment emergence and inclusion in summary tables, incomplete onset dates will be imputed as detailed in Appendix B.

AEs will be summarized by the number and percent of subjects in each primary SOC and preferred term. Patients will be counted only once for each primary SOC and each preferred term. Summary tables of AEs by primary SOC, preferred term and intensity will be provided. If a subject has more than one AE coded to the same preferred term, the subject will be counted only once for that preferred term by using the event with the highest intensity. Similarly, if a subject has more than one AE within a primary SOC category, the subject will be counted only once in that SOC category by using the event with the highest intensity. AEs by primary SOC, preferred term and relationship to study drug will be provided as well. If a subject has more than one AE coded to the same preferred term, the subject will be counted only once for that preferred term by using the most related event. Similarly, if a subject has more than one AE within a primary SOC category, the subject will be counted only once in that primary SOC category by using the most related event. In addition, serious adverse events (SAE) by primary SOC and preferred term will be provided. Deaths and SAEs will be summarized similarly to AEs. All adverse event tables will also include the total number of events, counting multiple events per patient.

AEs will be presented by treatment group (CAM2038 q1w of 24 mg or 32 mg and by hydromorphone treatment groups i.e., 0 mg 6 mg or 18 mg – during qualification period- and CAMP2038 relevant dose/hydromorphone relevant dose – on the days of hydromorphone challenges) and overall. An AE will

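### Protocol 12.3.4.1 and SAP 11.2 end the treatment-emergent window on different days, and the SAP does not say which drug its last dose means

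*Protocol*

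**What the plan says.** The protocol splits its definition of a treatment-emergent adverse event (TEAE) by seriousness (12.3.4.1). The first part covers "Non-serious AEs with onset on the date of first dose of treatment with the study drug through discharge or Early Termination". The second covers "Serious AEs with onset on the date of first dose of treatment with the study drug through 30 days after discharge or Early Termination". A third part, for events that begin before treatment and then worsen, also stops at discharge or early termination.

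SAP 11.2 has no such split and does not mention discharge: "Only TEAEs with an onset date prior to date of last dose + 30 days will be tabulated in summary tables". It does not define the last dose.

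Collection is a separate rule. Protocol 10.4.1.1 states: "All AEs will be documented and followed from the time the subject has signed the ICF until 14 days after the Follow-up Visit". For a subject who terminates early, the limit is instead 30 days from termination. Section 10.4.1.2.1 requires all SAEs to be reported over the same period; after it, only those considered possibly related.

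The schedule fixes the calendar. CAM2038 is given as "injections on Day 0 and Day 7", and the last hydromorphone challenge session is Days 11 to 13. "Subjects will be discharged on Day 14 and a follow-up phone interview will be conducted on approximately Day 21". Section 7.1.5 says the call is to obtain information on safety issues, and it expects plasma buprenorphine of about 1.4 to 1.8 ng/mL after Day 14.

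**The concern.** Both documents say which adverse events belong in the treatment-emergent tables, and they give different answers. Safety and tolerability is a secondary objective (protocol 6.2), so the event counts in the report should not depend on which document is programmed.

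The protocol's non-serious rule also conflicts with the protocol's own follow-up. It closes on the day of discharge, when 7.1.5 still expects measurable drug. A new non-serious event in the week after discharge, reported at the call arranged to ask about safety, could not be treatment-emergent.

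The SAP's rule avoids that problem and creates two smaller ones. It ends earlier than the protocol's window for serious events. It is also anchored to a dose, while collection is anchored to the follow-up call or to early termination, so some events can be collected and then cut from the tables.

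**Working it through.** Inputs for a completer (protocol 7.1): last CAM2038 Day 7, last hydromorphone Day 13, discharge Day 14. The plan's own figure for the call reproduces: 14 + 7 = Day 21.

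**End of each window, completer**

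| Rule | Formula | Result |
|---|---|---|
| Protocol 12.3.4.1, non-serious TEAE | discharge | Day 14 |
| Protocol 12.3.4.1, serious TEAE | 14 + 30 | Day 44 |
| Protocol 10.4.1.1 and 10.4.1.2.1, collection | 21 + 14 | Day 35 |
| SAP 11.2, last dose = CAM2038 | onset before 7 + 30 = 37 | last onset Day 36 |
| SAP 11.2, last dose = hydromorphone | onset before 13 + 30 = 43 | last onset Day 42 |

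**Where the two TEAE rules disagree, completer**

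- Non-serious, onset Days 15 to 21, reported at the call: not a TEAE under the protocol; tabulated under either reading of the SAP.
- Serious, onset Days 37 to 44: a TEAE under the protocol; not tabulated under the SAP counted from CAM2038. Counted from hydromorphone, the excluded days are 43 and 44.
- After Day 35 only possibly related SAEs need be reported, so few events should fall in that range.

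**Is a completer's routine collection fully tabulated under the SAP?** Collection ends on Day 35 and the last tabulated onset, counted from CAM2038, is Day 36, so yes. The margin is thin. If the call is made on Day c, collection ends on c + 14, which stays within Day 36 only if c is 22 or less. The call is set for approximately Day 21.

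**Early terminators.** Let the last depot be on Day d and termination on Day e. Collection and the protocol's serious window both end on e + 30. The SAP, counted from CAM2038, excludes onsets from d + 30. The days collected but not tabulated are d + 30 to e + 30, which is e − d + 1 days.

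- Example, d = 0 and e = 5: protocol non-serious window ends Day 5; collection runs to Day 35; SAP cut-off is Day 30. Onsets on Days 30 to 35 (6 days) are collected and then dropped from the tables.
- If hydromorphone on Day 5 counts as the last dose, the cut-off is Day 35 and only an onset on Day 35 itself is lost.

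**The case against.** The strongest reply is that the SAP governs. Protocol section 12 says its methods may be revised and that the final analysis plan is the SAP. On that reading the Day 14 cut-off is never applied, and a completer's routinely collected events all reach the tables. This stands, and it removes most of the practical harm. A reader might infer from 12.3.4.1 that events reported at the follow-up call will be excluded and post-discharge harm under-counted; that follows only if the protocol's definition is programmed. In addition, SAP 6.0 lists all CRF data, so a collected event left out of the tables is still reported. What the reply does not settle is the undefined last dose, the serious events on Days 37 to 44 and the early-terminator gap. Nor does the SAP say that it replaces 12.3.4.1.

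Other stronger readings also go too far:

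- **Several competing end dates.** Day 35 is a collection and reporting limit, and Days 14 and 44 are two parts of one definition. Collection and tabulation windows may differ. The direct conflict is between 12.3.4.1 and SAP 11.2.
- **Early terminators lost at peak concentration.** Only the protocol's non-serious rule does this. Events are collected to 30 days after termination, 8.4 asks for efforts to continue safety assessments after study drug is stopped, and the SAP tabulates to 30 days after the last dose.
- **Most of the wash-out follows the call.** Assuming mono-exponential decline, the 24 mg troughs in Tables 2 and 3 give an accumulation ratio of 1.4/0.86 = 1.63, so 1 − 1/1.63 = 39% of the Day 14 level remains on Day 21. Half-lives of about 63 to 74 hours, from Tables 1 and 2, leave 16% to 21%. On either basis, 61% to 84% has gone by the call.
- **A missing contact after Day 21.** Table 4 schedules none, but there is a call 14 days after the last depot, and possibly related SAEs stay reportable with no end date. A further call is a preference.

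**Conclusion.** The two documents end the TEAE window differently, and the SAP's rule is incomplete because the last dose is not identified. For a completer, the last countable onset is Day 14 (protocol) against Day 36 or 42 (SAP) for non-serious events, and Day 44 against Day 36 or 42 for serious events.

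If the SAP governs and counts from CAM2038, the loss from the tables is confined to two groups: SAEs starting on Days 37 to 44, and early-terminator events starting on or after last dose plus 30 days but within the collection period. This assumes discharge on Day 14 and a call no later than Day 22. It is a point to correct before database lock, at low cost, and not evidence that post-discharge safety will be substantially under-counted.

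The case for moving the non-serious cut-off past discharge needs no pharmacokinetic model; the expected level in 7.1.5 and the existence of the call are enough. Withdrawal symptoms are not recorded as AEs (10.4.1.1), so no change to this window will count them.

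**What to change.** Use one TEAE definition in protocol 12.3.4.1 and SAP 11.2:

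- Remove discharge or early termination as the cut-off for non-serious events, and for events that worsen on treatment.
- If a dose anchor is kept, state whether the last dose is CAM2038 or hydromorphone.
- Set the end of tabulation no earlier than the end of collection in 10.4.1.1: 14 days after the follow-up call, or 30 days after early termination.
- For SAEs, set it no earlier than the existing 30 days after discharge or early termination.

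Copying the SAP's present rule into the protocol would not meet these limits. Last CAM2038 dose plus 30 days would bring the serious cut-off forward from Day 44 to Day 37 and would leave the early-terminator gap open. Counted from hydromorphone, it would still miss serious onsets on Days 43 and 44.

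The cost is wording in two sections, the matching table programming, and slightly higher AE counts. A further phone contact after Day 21 is optional and is not part of this correction.

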# 12.3.4.2. Clinical Laboratory Evaluations

For continuous laboratory parameters, descriptive statistics will be presented for each visit and for the changes from Baseline to each subsequent visit by treatment group (CAM2038 q1w of 24 mg or 32 mg).

Additionally, clinical laboratory parameters will be categorized as low, normal, or high according to laboratory range specifications and the number and percentage of subjects in each category will be presented in shift tables.

Laboratory values that are outside the normal range will also be flagged in the data listings, along with corresponding normal ranges.

# **12.3.4.3.** Vital Signs

Descriptive summaries (mean, SD, median, minimum, and maximum) of actual values and changes from Baseline will be calculated for systolic blood pressure, diastolic blood pressure, heart rate, respiratory rate, and oral body temperature.

# 12.3.4.4. Physical Examination Findings

Physical examination data will be presented in the listings.

